7.8.3 Laboratory Data

For Hematology and Serum Chemistry, descriptive statistics of actual values and change from baseline for each laboratory parameter will be presented by timepoint and surgery type. Analyses will be performed based on the Safety Population. Data will then be categorized into the following status categories using the laboratory reference ranges: low (below lower limit of normal), normal, and high (above upper limit of normal). Shift tables summarizing changes in status from baseline to each post-baseline timepoint will be presented.

Serology and Coagulation are only collected at screening. These results will be summarized descriptively including percentage of normal/abnormal values for coagulation and percentage of positive/negative/not done for serology. For coagulation, separate summaries will be created for Local and Central laboratory results.

For urinalysis, the percentage of normal, abnormal and not clinically significant, abnormal and clinically significant, and not done will be summarized by timepoint and surgery type.

Data listings will be produced for all collected laboratory data including hematology, serum chemistry, coagulation serology, and urinalysis. Laboratory values outside the laboratory's normal ranges will be flagged as H (high, above normal) or L (low, below normal) in laboratory data listings.

7.8.4 Vital Signs and Other Safety Parameters

Descriptive statistics for the actual value at each timepoint and the change from baseline to each post baseline timepoint in SBP and DBP, heart rate, respiratory rate, and body temperature will be summarized by surgery type and overall. Analyses will be performed based on the Safety Population.

A data listing for vital signs (including body weight) will be produced.

Physical examination findings results will be summarized by percentage of normal/abnormal findings at each timepoint by surgery type and overall for the Safety Population.

Body weight will be summarized descriptively at each timepoint by surgery type and overall for the Safety Population.

Data listings will be created for Physical Examination and ECG.

7.9 Other Endpoints and Analysis

All the analyses in this section will be stratified by surgery type and overall. The Safety Population will be used for all the analyses described in this section.

7.9.1 Immunogenicity

Immunogenicity results (anti-LR769 antibodies and anti-host related impurities antibodies) will be analyzed descriptively by timepoint and surgery type for the Safety Population. No statistical hypothesis testing will be performed.

A data listing of immunogenicity data will be created.

7.9.2 Concomitant Medications

Concomitant medications will be coded with WHO DD providing ATC2 and ATC4 codes, and PT for each medication. A medication will be considered concomitant if it has started during the treatment period, or if it has started prior to the first treatment and ended within the treatment period. The number and percentage of patients taking concomitant medications will be summarized by surgery type and overall and by ATC codes for the Safety Population.

A data listing of concomitant medications will be provided.

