5.5 Concomitant Therapy

All concomitant therapies, including the use of blood products such as red blood cells, platelets, fresh frozen plasma, fibrinogen, etc, will be recorded in the patients' medical records and/or patients' diaries and in the eCRF. Concomitant therapies, including date, time, and dose, will be recorded from 30 days prior to screening and throughout the study until the end of the follow-up period.

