5.6 Restrictions

5.6.1 Prohibited Medications

All aspirin, NSAIDs, herbs, natural medications, or any other drug with platelet inhibitory properties must be discontinued at least 1 week prior to elective surgical or other invasive procedure and for the duration of treatment with LR769.

Additional restrictions to concomitant therapies include the use of other sources of FVIIa, such as aPCC (FEIBA[®]) or NovoSeven[®]. These products may be used only if the response to LR769 is considered insufficient (ie, treatment failure), in which case these bypassing agents may be used for rescue therapy.

Other agents for the prevention of excessive bleeding during surgical or other invasive procedures, such as antifibrinolytics, are allowed and will be recorded on the eCRF.

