6.13 Removal of Patients from the Trial or Treatment

The investigator may withdraw a patient from the study for any of the following reasons:

- The investigator believes it is in the best interest of the patient to discontinue the study
- The Sponsor or investigator terminates the study
- The patient withdraws consent or requests to be discontinued from the study
- The patient is non-compliant

In case of early withdrawal of the patient, he will be asked to perform the 48 (\pm 4) hour visit assessment after last administration of LR769, unless he has withdrawn Informed Consent.

The investigator may discontinue a patient from LR769 treatment for any of the following reasons:

- AE or SAE possibly related to LR769 treatment
- A clinically significant change in the patient's condition that does not allow safe administration of LR769
- Per judgment of the investigator, if an adequate hemostatic response is not achieved with LR769, and the bleeding requires continued treatment, the treating physician should stop treatment with LR769 and treat the patient with a rescue therapy, such as another bypassing agent (e.g., FEIBA® or NovoSeven®) and/or other effective hemostatic treatment. The patient remains eligible for treatment with LR769 for a new surgical procedure taking into account the pharmacodynamic half-life of the rescue therapy given.

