7.3 Handling of Missing Data

Any imputation of missing or incomplete data will be flagged in the analysis datasets. The original value will be kept for traceability.

Missing Final Assessment of Postoperative Response (48 [\pm 4] hours after the last dose of LR769)

In accordance with the definition of postoperative assessment in section 6.8 of the Protocol, missing final postoperative assessment of treatment response by the investigator will be imputed to "Poor", if and only if, both of the following conditions are satisfied: (1) patient was withdrawn from study, within 2 days after the last dose of LR769, due to adverse event or by Investigator's decision and (2) rescue therapy (any medication in antihemorrhagics ATC subgroup) was used within 52 hours after the last dose of LR769.

Incomplete/Missing Dates

Dates of historical events such as the date of diagnosis, date of onset, start/stop dates of previous treatment, start dates of medical conditions, etc. will be imputed when partial dates are collected. In case of missing month and day and available year YYYY the corresponding date will be replaced with "01JULYYYY". In case of missing day the date will be replaced with "15MMMYYYY".

The following rules will be applied for AEs and concomitant medications with incomplete dates:

- If Day is missing for Start Date and Month and Year are the same as Month and Year for the First Treatment Date, then Start Date equals First Treatment Date.
- If Day is missing for Start Date and Month and Year are not the same as Month and Year for the First Treatment Date, then impute Day 1 of the month.
- If Day and Month are missing for Start Date and the Year is the same as the Year for the First Treatment Date, then Start Date equals First Treatment Date.
- If Day and Month are missing for Start Date and the Year is not the same as the Year for the First Treatment Date, then impute July 1st of the year.

- If the Start Date is missing entirely, impute the start date with minimum between the End date of AE and First Treatment Date. Therefore, if an AE with missing start date has ended before the start of the treatment, the Start Date will be imputed with the End Date, and if the AE in question ended after the First Treatment Date, then the Start Date will be imputed with the First Treatment Date.

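### On its ordinary reading, SAP 7.9.2 leaves drugs started after the last LR769 dose, including rescue given once LR769 is stopped, out of the only concomitant-medication summary

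*SAP*

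**What the plan says.** SAP 7.9.2 gives two routes into the concomitant-medication table. The first is by start date: "A medication will be considered concomitant if it has started during the treatment period". The second is for earlier starts: "if it has started prior to the first treatment and ended within the treatment period". The summary is built on that definition: "The number and percentage of patients taking concomitant medications will be summarized by surgery type and overall and by ATC codes". The section adds that "A data listing of concomitant medications will be provided", and SAP 7.1 promises listings of everything collected. The SAP does not define the treatment period.

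Other sections bear on what this leaves out:

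- Protocol 5.5 says that concomitant therapies "will be recorded from 30 days prior to screening and throughout the study until the end of the follow-up period".
- Protocol 6.13 says that, if hemostasis is inadequate and bleeding needs continued treatment, "the treating physician should stop treatment with LR769 and treat the patient with a rescue therapy".
- SAP 7.3 makes it one condition for imputing a missing final rating as Poor that "rescue therapy (any medication in antihemorrhagics ATC subgroup) was used within 52 hours after the last dose of LR769".
- Protocol 5.6.1 restricts platelet-inhibiting drugs before the procedure and "for the duration of treatment with LR769".
- SAP 7.6.4, the only other medication summary described, covers previous bleeding medications and previous immune tolerance medications.

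**The concern.** The two assessments that matter most come after the last dose. The primary rating is made 48 (±4) hours after it, and adverse events, including thromboembolic events, are analyzed to 28 (±3) days after it. A bypassing agent, a platelet-inhibiting drug or an antithrombotic begun in those intervals could influence the hemostasis being rated or confound a safety event. If the medication table stops at the last dose, it covers a shorter period than the efficacy and adverse-event tables it should help interpret. This is a single-arm, open-label trial planned for at least 12 procedures, so a reader will want to see in a table how often another hemostatic agent was needed.

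**Working it through.** The plan states no figure on this point, so there is none to reproduce. The check applies the rule to cases.

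**Meaning of the treatment period.** Protocol Appendix 1 places the 48-hour and 28-day visits under follow-up, apart from LR769 treatment. Protocol 5.5 names a follow-up period of its own. The ordinary reading is therefore first to last LR769 dose, and this is an assumption.

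**Rule.** Put the first dose at 0 and the last at L hours. A drug with start s and end e is counted if 0 ≤ s ≤ L, or if s < 0 and 0 ≤ e ≤ L.

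**Inputs.** L = 48 for the 2-day minimum in minor procedures (protocol 5.2.3) and L = 120 for the 5-day minimum in major procedures (protocol 5.2.2). The results are the same for both.

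| Case | Counted? |
|---|---|
| Started within the period | Yes |
| Started before, ended within | Yes |
| Started before, ended after the last dose | No |
| Rescue started 2 h after the last dose | No |
| Rescue started 51 h after the last dose | No |
| Drug started 20 days after the last dose | No |

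**Comparison with SAP 7.3.** Both rescue cases lie inside the 52-hour window that SAP 7.3 searches (48 + 4 = 52). The SAP thus expects rescue after the last dose, but its medication table excludes it there.

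**Comparison with SAP 7.6.2.** For medical conditions the SAP uses an overlap rule: start before the last injection, and end after the first injection or missing. A condition that outlasts treatment is kept. Under 7.9.2 a drug with the same dates is lost.

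**Other planned output.**

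- The Poor category can rest on rescue, but also on transfusion more than 2-fold above expectation, hypotension or unexpected transfer to intensive care. It does not identify rescue.
- SAP 7.3 uses rescue only when the final rating is missing and the patient was also withdrawn within 2 days of the last dose for an adverse event or by investigator decision. It plans no tabulation.
- The secondary endpoints in SAP 7.7.2 count transfusion events, bleeding episodes and re-explorations to 48 (±4) hours. They do not count bypassing agents.

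**Elapsed time after the last dose,** as a share of first dose to end of follow-up:

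- 2-day course: 28/(2 + 28) = 93.3%, or 92.6% to 93.9% for follow-up of 25 to 31 days.
- 5-day course: 28/(5 + 28) = 84.8%, or 83.3% to 86.1%.
- 14-day course: 28/(14 + 28) = 66.7%.

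**The case against.** The strongest reply is that the point turns on an undefined term. In Appendix 1 the treatment heading appears to span the visit 7 to 14 days after the first dose, which for a 2-day course falls after the last dose. SAP 7.6.2 refers to the last injection when it means that, and 7.9.2 uses a different term. This stands as a caveat. If the period were meant to run to the end of follow-up, later starts would be counted. The SAP would still have to say so, and a drug begun before the first dose and outlasting the period would still be missed.

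It is also fair that nothing is lost from the data. Listings keep every drug, and at the minimum of 12 procedures they could be read in full. Need for rescue feeds the tabulated Poor ratings, and transfusions have their own summary. The table shells are a separate document that could not be checked.

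Three stronger readings are tempting, and the documents support none of them:

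- **That all rescue is left out, so the table would show none.** Protocol 5.6.1 allows other bypassing agents when response is insufficient without itself requiring that LR769 be stopped first. Rescue begun before the final LR769 dose would be counted. So might rescue begun on the same calendar day, since the SAP does not say whether dates or times are compared.
- **That 85% to 93% of drugs are missed.** Those shares are elapsed time at minimum treatment duration. Drug starts need not be spread evenly over time, and longer courses lower the shares.
- **That SAP section 9 should have declared a deviation.** Protocol 5.5 and 6.11 govern recording. Protocol section 9 plans no specific concomitant-medication analysis from which the SAP could depart.

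**Conclusion.** The point holds as a gap in a summary table. On the ordinary reading, non-transfusion drugs started after the last LR769 dose, and drugs begun before the first dose that outlast the period, are absent from the only concomitant-medication summary and visible only in listings. For later starts, the uncovered span is the full 44 to 52 hours before the primary rating and the 25 to 31 days of safety follow-up, whatever the treatment duration. The documents give no rescue rate or medication counts, so the number of drugs affected cannot be estimated.

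The primary success proportion does not change. The conclusion assumes that the treatment period ends at the last dose and that the unseen table shells add no rescue summary. It should be corrected, but it does not threaten the main result.

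**What to change.** Reword SAP 7.9.2 as follows:

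1. A medication is concomitant for a procedure if it was used at any time from that procedure's first LR769 dose to its 28 (±3)-day visit. This avoids the undefined term and captures drugs already running before the first dose.
2. Flag medications started after the last LR769 dose, separating at least those started up to the 48-hour assessment from those started after it.
3. Add a per-procedure row for hemostatic rescue agents (bypassing agents, porcine FVIII), whether started before or after the last LR769 dose.

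The cost is revised SAP wording and a longer table. Dates and times are already collected under protocol 5.5 and 6.11, so no new data are needed.

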8. INTERIM ANALYSIS

There are no planned interim analyses for this study.

9. DEVIATIONS FROM ANALYSIS AS DESCRIBED IN THE PROTOCOL

Protocol Section 9.6 specifies that two-sided paired t-tests will be used to test whether the mean changes from baseline equal 0 for laboratory and immunogenicity data as well as for vital signs. These tests will not be performed as they are deemed unnecessary.

10. PROGRAMMING SPECIFICATIONS

All outputs will be produced using SAS version 9.4 or a later version.

The margins should be at least 1.50 inches for the binding edge and 1.0 inches for all others.

In the top left portion of each table/listing, the protocol number will be presented. On the next line a table/listing number followed by the title of the table/listing and population information will be displayed. A blank horizontal line will appear after the column headings of the table/listing. Footnotes will be put under the main body of text at the bottom of the page. The source listing number will be displayed for all tables. The SAS program name will appear bottom left in a string and the page number will appear on the bottom right corner of each table/listing. The date and time of creation of table/listing will appear bottom left under the SAS program name line.

Courier New 8-point bold font will be used for all tables and listings. Landscape layout will be used for both tables and listings, SAS page settings linesize=137 and pagesize=47 will be used. Any date information in the listing will use the date9. format, for example, 07MAY2002.

All outputs will be provided in the PDF (text) and in the RTF (columnar) formats.

The International Council for Harmonisation (ICH) numbering will be used for all tables, figures and data listings.

Missing values for both numeric and character variables will be presented as blanks in data listings. In tables, a zero (0) may be used if appropriate to identify when the frequency of non-missing observations for a variable is 0.

All observed time values will be presented using a 24-hour clock HH:MM format (e.g. 15:26).

Time durations will be reported in HH:MM notation. The use of decimal notation to present (display) time durations should be avoided (e.g. 0.083h = 5m) unless it is necessary to show the computation of time differences in a table, figure, or data listing, in which case both notations may be used to display the time duration.

11. TABLES, LISTINGS, AND FIGURES

A detailed list of tables, figures and listings (TFLs) is prepared and maintained as a separate document – TFL shells.

